# GENERAL STUDY INFORMATION

Use for greater than minimal risk studies and minimal risk studies that fit into one or more expedited categories (see Section 5.3 of our Policies & Procedures for details regarding expedited research).

Do NOT submit this form if the study will qualify for exempt review, instead submit HRP-UT902 IRB Proposal – Exempt Submission Form found in the document Library.

If you are only using secondary data that will not be initially collected solely for this research project, use HRP-UT903 Template IRB Proposal Secondary Use form instead.

For studies following a multi-center or sponsor protocol, please use this guidance to assist in your completion of this form.

For questions regarding definitions, policies, or terms referenced below see the policies and procedures manual.

Please note, Word online does not support Word checkboxes. Please download the file and use your desktop version of Microsoft Word.

# **1** Review Type (Choose one)

*Click on the check box (or double click and type an "X" if using Google Docs) the one review type that applies.* 

Please note: Expedited Review does not refer to the timeliness of the review of your protocol, but specific categories of research defined by ORHP. If you would like help determining which type of review is most appropriate for your study please contact the Office of Research Support and Compliance: https://research.utexas.edu/ors/about-ors/contact-us/.

- a 🔲 Full Board Review Greater than Minimal Risk Research
- **b** Z Expedited Review Minimal Risk Research

# **2** Research Hypothesis

To input text, click in the light grey area below.

A program of empathetic and relationship-oriented telephone calls by lightly trained lay persons can support diabetes self-management behaviors and reduce Hemoglobin A1C in diabetic patients of a federally qualified health center (FQHC).

Mental health issues affect an individual's ability to manage chronic health conditions such as diabetes (Chaoyang et al 2008; Schmitt et al 2021). In self-management programs for diabetes, when mental health is addressed it is usually secondary to more tactical self-management steps such as goal-setting and providing connection to resources. In this study we will assess a mental-health-first approach to supporting diabetes self-management through a program of empathetic telephone calls, delivered by lightly-trained lay people. The program builds on the success of a previously tested 4-week long empathetic telephone call program that found significant and sizeable reductions in depression, anxiety and general mental health (Kahlon et al 2021).

Prior work has shown that telephone-based diabetes education and support programs can significantly improve Hemoglobin A1C management, reducing levels in low income diverse communities. A program of 8 telephone calls over 12 months implemented in the Bronx, NY focusing primarily on medication adherence and secondarily on nutrition and exercise support achieved significant reductions of 0.8% relative to controls for those who began the program with A1C levels above 9% (Chamani et al 2015) A follow-up analysis showed that the intervention reduced hospitalization over the following three years (Tahbaei et al 2020).

In this study we will use a randomized controlled trial to assess the impact of a 6-month long intervention of empathetic relationship building engagement with emotional and motivational support delivered telephonically for patients with diabetes at a Federally Qualified Health Center (FQHC). Telephone callers, lay people with light training on how to be empathetic and engaging in calls, will support participants' journeys on their own goals related to nutrition, exercise, sleep and medication adherence. They will not provide diabetes specific information, instead they will support people walking more, sleeping better, eating better and taking their medications. The impact of the program will be assessed primarily on Hemoglobin A1C levels and secondarily on depression and mental health at the end of the 6-month intervention, and in the following 6 months. Results will be compared to patients in the control arm that receive usual care. Participants will be recruited from our partner, an FQHC, Lone Star Circle of Care (LSCC) and include patients with Hemoglobin A1C of greater than 8.0 as measured at any point in the 12 months preceding enrollment.

- Chaoyang Li, Earl S. Ford, Tara W. Strine, Ali H. Mokdad. Prevalence of Depression Among U.S. Adults With Diabetes Diabetes Care Jan 2008, 31 (1) 105-107; DOI: 10.2337/dc07-1154
- Kahlon MK, Aksan N, Aubrey R, et al. Effect of Layperson-Delivered, Empathy-Focused Program of Telephone Calls on Loneliness, Depression, and Anxiety Among Adults During the COVID-19

Pandemic: A Randomized Clinical Trial. JAMA Psychiatry. 2021;78(6):616–622. doi:10.1001/jamapsychiatry.2021.0113

- Impact of a Telephonic Intervention to Improve Diabetes Control on Health Care Utilization and Cost for Adults in South Bronx, New York
- Bahman P. Tabaei, Renata E. Howland, Jeffrey S. Gonzalez, Shadi Chamany, Elizabeth A. Walker, Clyde B. Schechter, Winfred Y. Wu Impact of a Telephonic Intervention to Improve Diabetes Control on Health Care Utilization and Cost for Adults in South Bronx, New York. Diabetes Care Apr 2020, 43 (4) 743-750; DOI: 10.2337/dc19-0954

# **4** Design and Methodology

Provide information regarding study design or data collection methodologies. Details regarding protocol specific research procedures will be discussed in a later section.

#### To input text, click in the light grey area below.

Design: Randomized controlled trial.

**Population**: Adults with Hemoglobin A1C >8.0 measured at any point in the 12 months prior to enrollment, who have had at least one visit (Family medicine, behavioral health or other) with Lone Star Circle of Care within the past 12 months (in person or telehealth)

**Randomization:** Consented participants will be randomized to the intervention or control arm in a 1:1 ratio.

[figure not shown]
**Blinding:** Research staff involved in taking biomedical measurements will be blinded to participant status. Participants will complete surveys in person using a tablet or individual paper copy, thus research associates will remain blinded.

Time period: The study is divided into two parts.

- *Phase 1 (6 months)* is a randomized controlled trial testing the effect of telephone call-based empathetic engagement supported by caller-customized letters, together with small self-selected incentives (health tool) and caller-selected personal recognitions (small gifts selected based on the callers understanding of the participant), and low-literacy basic diabetes self-management information, against usual care. The primary outcome is Hemoglobin A1C (A1C) with repeated measures at baseline, 3 and 6 months.
- *Phase 2 (subsequent 6 months)* is the follow-up phase allowing us to *estimate* the 12 month longer term trajectory of A1C in Intervention and Control. To maximize the utility of the study to inform the most effective program design, participants in the control arm will receive the same opportunity to self-select health tool as the intervention arm received in Phase 1, but will make the choice during the 6

month survey collection. The material portion of the recognition/gifts, which (gift), will also be selected at the 6-month survey, but instead of being selected by the caller, the participant will select their own gift from the same set used by the callers in Phase 1. The control arm will also receive the low-literacy basic diabetes self-management information during Phase 2. All items will be provided to the control arm in Phase 2 on the similar schedule as intervention participants received them in Phase 1. As a result, we hope to *estimate* the impact of the small incentives and basic diabetes self-management information without the communication elements, telephone call-based empathetic engagement and customized newsletters, by comparing the results in the Intervention arm in Phase 1, with those in the Control arm in Phase 2.

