#### **Overview:**

Intervention: Participants in the intervention arm receive -

- Incentives & personal recognitions
- Small Health-promoting Incentive:
  - Choice of a health-promoting tool offered by the caller in the first week of the program. A choice will be provided by the caller between a pedometer and a smart weigh scale of equivalent value. If neither of these options are applicable based on health or other limitations, back-up options will be offered to them (fitness resistant bands or exercise program for upper body fitness). The health-promoting tool will be mailed to participants by approximately the 5th week of the program.
- Personalized recognition of participant by caller ("Personal recognition/Gift"):
  - Callers will select, based on their understanding of the participant, 2 items from a larger pre-selected set of health-related items (related to cooking,

physical activity or sleep), each of equivalent ~\$25.00 value. Callers will select and the program will mail items to the participants between months 1 and 5, to ensure the second item is received within 6 months (Phase 1). Callers will have a deadline to send the first item by the middle of the third month (Month 2.5) and by the middle of the 5th month (Month 4.5)

- Diabetes management information (print) geared to people with low-literacy (Diabetes management materials). This information will be mailed to intervention participants after randomization.
- Communications to support and celebrate the participants learnings:

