For phase-II of the study, we have the opportunity to estimate two effects of interest including: a) the effect of the incentive and materials provision (2-selected items and health tool) on A1c among controls in phase-II over a period of 6-months compared to its effects when such provisions are coupled with empathy calls among intervention participants in phase-I (a between group effect estimate), b) the effects of exposure periods (phase-I and phase-II) on A1c and depression from baseline through 12-months separately for the two groups. In the case of the intervention group, the phase-I to phase-II difference gives clues to sustainability and in the case of the control group, the phase-I to phase-II difference provides a within-person estimate of the effect of incentive provision

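### Intervention Phase 1 versus control Phase 2 measures what the calls and letters add to the materials, not the effect of the materials, so its label in Section 4 needs correcting

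*Combined protocol and SAP*

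**What the plan says.** Section 4, Phase 2, gives the aim as estimating the "impact of the small incentives and basic diabetes self-management information without the communication elements", and names the contrast: "by comparing the results in the Intervention arm in Phase 1, with those in the Control arm in Phase 2".

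What each cell receives is set out in Sections 4 and 11:

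- **Intervention, Phase 1.** Calls and letters, "together with small self-selected incentives (health tool) and caller-selected personal recognitions". The print information is supplied too: "This information will be mailed to intervention participants after randomization".
- **Control, Phase 1.** Usual care only (Section 11, Control arm).
- **Control, Phase 2.** On the materials as a whole, Section 4 states: "All items will be provided to the control arm in Phase 2 on the similar schedule as intervention participants received them in Phase 1". On the print information: "The control arm will also receive the low-literacy basic diabetes self-management information during Phase 2". The Overview in Section 4 says that controls get no calls or letters.

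The last paragraph of Section 5 (Data Analysis) lists two phase-II effects. Item (a) opens as the effect of the incentives and materials among controls in phase II, but then sets it against the intervention arm: "compared to its effects when such provisions are coupled with empathy calls among intervention participants in phase-I (a between group effect estimate". Item (b) turns to the control arm alone, where "the phase-I to phase-II difference provides a within-person estimate of the effect of incentive provision".

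**The concern.** A contrast between two cells can estimate the effect of a component only if the cells differ in that component. The two cells named in Section 4 both have the materials and differ in the communication elements, so the label and the contrast do not match. Section 5(b) ties essentially the same effect to a different contrast.

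Section 4 gives the choice of an effective program design as the reason for supplying controls in Phase 2, so separating materials from calls is the purpose of this step. Taken at its label, a difference near zero would suggest that the materials have no impact, when it would mean that the calls add nothing to them. A large difference would be credited to the materials, when it came from the communication elements.

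**Working it through.** The plan gives no effect size, power or sample size for the phase-II contrasts, so there is no stated figure to reproduce. The check is which effects each contrast contains.

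**Terms**, for the 6-month change in A1c within a phase:

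- M: materials (health tool, two gifts, print information)
- C: communication elements (calls and letters)
- I: interaction of materials with communication
- g: gifts chosen by the caller instead of by the participant
- s1, s2: background change in Phase 1 and Phase 2 (trend, regression to the mean)

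**Cells**, from Sections 4 and 11:

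- Intervention Phase 1 = M + C + I + g + s1
- Control Phase 1 = s1
- Control Phase 2 = M + s2

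**Contrasts:**

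- Section 4 and Section 5(a): (M + C + I + g + s1) - (M + s2) = C + I + g + (s1 - s2). The coefficient on M is 0.
- Section 5(b), control Phase 2 minus control Phase 1: (M + s2) - s1 = M + (s2 - s1). The coefficient on M is 1.
- Randomised, intervention Phase 1 minus control Phase 1: M + C + I + g. No period term.

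Subtracting the first contrast from the third gives M + (s2 - s1), which is the second. Within this design the materials effect can be reached only through the within-control contrast.

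The result does not depend on using change scores. If the results compared are A1c levels at the end of each phase, with b the common baseline mean under randomisation, then (b + s1 + M + C + I + g) - (b + s1 + M + s2) = C + I + g - s2. M is again absent.

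**Illustration.** All effect values are assumptions; none is in the plan. C = -0.4, I = g = 0.

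| M | Cross-phase, s1 = s2 = 0 | Within-control, s1 = s2 = 0 | Cross-phase, s1 = -0.3, s2 = 0 | Within-control, s1 = -0.3, s2 = 0 |
|---|---|---|---|---|
| 0 | -0.4 | 0.0 | -0.7 | 0.3 |
| -0.1 | -0.4 | -0.1 | -0.7 | 0.2 |
| -0.3 | -0.4 | -0.3 | -0.7 | 0.0 |
| -0.5 | -0.4 | -0.5 | -0.7 | -0.2 |

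The cross-phase contrast does not move with M. The within-control contrast follows M, but a Phase 1 background fall of 0.3 shifts it by +0.3, enough to hide a materials effect of -0.3 completely. The same fall makes communication look 0.3 better in the cross-phase contrast.

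A background fall in Phase 1 is plausible. Section 13d requires A1c of at least 7.5 at the baseline measurement and a value of 8.0 at least once in the prior 12 months, and Section 19 treats a baseline value under 7.5 as a screen failure. The baseline reading is both the entry test and the starting point of the Phase 1 change. The month-6 reading that starts Phase 2 is not selected in this way.

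**The case against.** The best defence is that Section 4 is compressed, not mistaken. On that view control Phase 2 shows the materials without communication, and intervention Phase 1 is only the benchmark. Section 5(a) supports this, because its wording amounts to materials alone against materials coupled with calls. This stands in part. A reader might infer that Section 5 as a whole contradicts Section 4, but it carries both contrasts: (a) is the Section 4 comparison, and the mismatch is with (b). Even so, (a) opens under the label of the incentive and materials effect, and the Section 4 sentence as written names an effect that its contrast does not contain.

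A reader might also infer that the trial will report the wrong component as effective. The documents do not support this. They give no test, threshold or reading rule for the contrast, and (a) makes the coupling with calls visible. The risk of misreading is real, but its occurrence and its size are conjecture.

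A further inference would be that the parenthesis in Section 5(a), which lists the two items and the health tool, removes the print information from the bundle. The governing phrase there also mentions materials, and Section 4 calls the print information by that word. The omission is minor and needs only a clearer list.

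Finally, the language is exploratory: Section 4 speaks of a hope to estimate, and Section 5 of an opportunity. That stands, and it limits the severity.

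**Conclusion.** The label in Section 4 is wrong as written. Intervention Phase 1 versus control Phase 2 contains no main effect of the materials. It estimates what the communication elements add to them, together with any interaction, caller selection of gifts and period difference. The exact cancellation assumes additive effects and the same materials on a comparable schedule in both cells; departures from these leave extra terms in the difference but do not bring the materials effect back.

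It would go too far to conclude that the within-control contrast in Section 5(b) is a sound estimate of the materials effect. It is the only one available here, but it equals M + (s2 - s1) and is exposed to regression to the mean. It would also be wrong to extend the point to the primary analysis: the randomised Phase 1 comparison contains no period term and is unaffected.

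The severity is minor: an exploratory aim with a misassigned label, which no figure in the documents allows to be sized beyond the illustration.

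**What to change.** - **Section 4 (Phase 2) and the opening label of Section 5(a):** describe intervention Phase 1 versus control Phase 2 as an exploratory, non-concurrent estimate of the added effect of the communication elements over the materials.
- **Section 4 and Section 5(b):** assign the materials effect to control Phase 2 versus control Phase 1. Define the bundle as the health tool, the two gifts and the print information, and name the result as the effect of that bundle.
- **Both contrasts:** state that they assume no period effect. For the within-control contrast, add that it may be distorted by regression to the mean because entry requires raised A1c.

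The cost is wording in two sections. No new data, visits or analyses are needed.

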We will test differences in the trajectory of A1c over the course of six-months with three assessments (baseline, 3- and 6-months) for those who receive empathy calls to support diabetes self-management versus those who do not receive these support calls. We will rely on linear mixed effect regressions with random terms to model individual differences in both the intercept and change terms, accounting for the clustering effect of shared lightly trained callers. We will predict these trajectories using the following person-level covariates: grouping indicator, terms to capture diabetic treatment type and dose, change in PHQ9 from baseline to 6-month depression. The cross-level interaction of grouping indicator with time will constitute the effect of interest. In addition, if change in depression predicts the person-specific slopes for A1c and does so more strongly for those in the intervention than control group, we would have evidence that depression management affects A1c course. Similar models will be constructed for the secondary outcome of depression, PHQ9 across three waves of data collection, with frequency/duration of support calls across those waves modeled as a time-varying covariate. Person-level covariates will include grouping indicator, terms to capture change in A1c from baseline to 6-months. If change in A1c predicts person-specific slopes for depression and does so more strongly for those in the intervention than control, we would have preliminary evidence that improved control of A1c affects course of depression, an unlikely outcome. The outcome of these mixed effect regressions will permit a preliminary estimate of the mediational role of depression on A1c management in phase-I. We will estimate those indirect effects using bootstrapped standard errors using the MPlus modeling framework for longitudinal change from baseline to 6-months. Healthcare utilization outcomes both self-reported and obtained from LSCC will be harmonized into a composite score of utilization. Depending on the distribution of each aspect of utilization (ER visits, hospitalization, PCP visits), we will construct models to predict differences between the intervention and control arm while covarying change in A1c and depression from baseline to 12-months.

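### The cross-period contrasts meant to separate materials from calls are not randomised and concurrent, and the plan does not say whether they compare A1c levels or changes; they should be descriptive

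*Combined protocol and SAP*

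**What the plan says.** Phase 1 randomises the whole package (calls, letters, health tool, gifts, printed information) against usual care. In Phase 2 the control arm receives the material items only.

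Two cross-period contrasts are planned.

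- **Intervention Phase 1 against control Phase 2.** Section 4 hopes to obtain the effect of the materials alone "by comparing the results in the Intervention arm in Phase 1, with those in the Control arm in Phase 2". Section 5 takes the Phase 2 effect of the items on control-arm A1c, measured across six months, and describes the contrast in these words: "compared to its effects when such provisions are coupled with empathy calls among intervention participants in phase-I (a between group effect estimate").
- **Control Phase 1 against control Phase 2.** Section 5 states that "in the case of the control group, the phase-I to phase-II difference provides a within-person estimate of the effect of incentive provision".

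On concurrent comparisons, the A1c model in section 5 stops at month 6: "We will test differences in the trajectory of A1c over the course of six-months with three assessments (baseline, 3- and 6-months"), and "The cross-level interaction of grouping indicator with time will constitute the effect of interest". The 12-month analysis is "on A1c and depression from baseline through 12-months separately for the two groups". The aims go further. Section 4 wants to estimate "the 12 month longer term trajectory of A1C in Intervention and Control", and the background under section 2 says that impact will also be assessed over the second six months and that results will be compared with the control arm.

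On entry, sections 13e and 19 exclude anyone whose baseline A1c is below 7.5, and section 13d also asks for a value of 8.0 at least once in the prior 12 months. Section 11 randomises after the baseline measures.

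**The concern.** The reading that opens Phase 1 is the one that had to reach 7.5. The month-6 reading that opens Phase 2 had no such condition. People selected for a high value tend to be lower at the next measurement without any treatment, and more of that fall comes in the first six months than in the second.

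If 6-month changes are compared, the intervention arm's Phase 1 change contains this fall while the control arm's Phase 2 change contains less of it or none. The difference looks like a benefit of calls. Within the control arm, a Phase 1 fall under usual care makes the later Phase 2 change look small, which tends to hide any benefit of the materials.

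Because Phase 1 randomises the package as a whole, these contrasts are the plan's stated route to the effect of materials without calls, and section 4 says that Phase 2 is meant to inform programme design.

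**Working it through.** **The plan's own figure.** There is none for these contrasts. The only correlation given is r = .30, in the power statement (sections 5 and 15). That statement reproduces as a group-by-time interaction with noncentrality f² × N × m / (1 − r), N = 300, m = 3, df 2 and 596. The smallest detectable f is .087 at 80% power and .099 at 90%, which round to the stated .09 and .10. The calculation concerns trial participants, so I read .30 as the correlation in the enrolled sample.

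**Inputs.** From the documents: baseline cut 7.5, prior cut 8.0, r = .30. Assumed: A1c before selection is normal with mean 8.5-9.0 and SD 1.5-2.0, and all true effects are zero. Two correlation patterns are used: constant over time, or decaying (12-month r equals 6-month r squared).

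**Closed form, 7.5 cut alone.** Let c = (7.5 − mean)/SD and d = SD × φ(c)/(1 − Φ(c)), the excess of the enrolled baseline mean over the population mean.

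- d = 0.641 (mean 8.5, SD 1.5), 1.018 (8.5, 2.0), 0.431 (9.0, 1.5), 0.779 (9.0, 2.0).
- Phase 1 change = −(1 − r6)d. Phase 2 change = −(r6 − r12)d.
- Spurious call benefit on the change reading = (1 − 2r6 + r12)d. This is (1 − r)d if r is constant and (1 − r)²d under decay.
- An enrolled r of .30 corresponds to a pre-selection r of .37-.41. Constant: 0.63 × 0.431 = 0.27 to 0.59 × 1.018 = 0.60. Decay: 0.63² × 0.431 = 0.17 to 0.59² × 1.018 = 0.35.

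**Both cuts, by simulation.** Keep cases with one prior reading of at least 8.0 and baseline of at least 7.5. Solve the pre-selection r so that the enrolled baseline-to-month-6 correlation equals the target. The decay column covers a prior reading 3 or 12 months before baseline.

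| Enrolled r | Spurious call benefit, constant | Spurious call benefit, decay |
|---|---|---|
| .30 | 0.20-0.42 | 0.19-0.46 |
| .50 | 0.10-0.20 | 0.10-0.17 |
| .70 | 0.04-0.08 | 0.03-0.05 |
| .85 | about 0.02 or less | about 0.02 or less |

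Example (mean 8.5, SD 2.0, enrolled r = .30):

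- Constant: enrolled means 9.73, 9.32 and 9.32 at months 0, 6 and 12. Changes are −0.41 and 0.00, so the spurious benefit is about 0.41.
- Decay, prior reading at 3 months: 9.79, 9.02 and 8.71. Changes are −0.77 and −0.31, so the spurious benefit is about 0.46.

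**Sensitivity.**

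- Mean widened to 8.0-9.5, r = .30: 0.14-0.48 (constant) or 0.13-0.52 (decay).
- Any of four prior readings may meet the 8.0 cut, r = .30: 0.26-0.54 or 0.18-0.38. With constant correlation, 0.15-0.29 at r = .50 and 0.07-0.13 at r = .70.
- r = .30 taken before selection, mean 7.5-8.5 and two prior readings: 0.36-0.96.

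**The other two readings.** Levels (intervention month 6 against control month 12), or the randomised Phase 1 effect set against control Phase 2 change, both leave (r6 − r12)d. That is zero if r is constant and r(1 − r)d against the calls under decay. With both cuts and enrolled r = .30 it is 0.11-0.31 under decay.

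**The case against.** The strongest reply is that the bias toward the calls exists on one reading of three. A six-month duration in section 5 is not an estimand. Section 2 speaks of A1c levels and section 4 names A1c at 6 months as primary, while section 5 models trajectories. This stands. A reader might infer that the plan is simply biased toward the calls, but the documents leave the choice open and do not support that.

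Second, the wording is partly hedged: section 4 expresses a hope, and section 5 speaks of an opportunity and, for the intervention arm, of clues. This also stands, so it would be wrong to say that the estimates are offered with no caution. Yet section 5 still labels the two figures a between-group effect estimate and a within-person estimate, and names no limitation.

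Third, a reader might infer that no concurrent comparison after month 6 was intended. Section 2 shows otherwise; what is missing is its specification in section 5.

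Fourth, subtracting the control arm's Phase 1 change might rescue the contrast. It does if the correlation is constant. Under decay it leaves a residual of opposite sign, with ratio r/(1 − r) to the original bias (7.5 cut alone). It therefore helps when the pre-selection r is below .5; at r = .7 the ratio is 0.7/0.3, about 2.3. It is usable as a sensitivity figure, not as a correction.

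**Conclusion.** The point holds in a conditional form and is of secondary importance. On every reading the cross-period contrasts are non-concurrent and cannot isolate calls or materials. On the change reading they also carry regression to the mean that favours the calls and works against the materials: about 0.2-0.5 A1c points at enrolled r = .30. For scale, section 2 cites a 0.8-point reduction in an earlier telephone programme among people starting above 9%. The artefact falls to 0.1-0.2 at r = .5, under 0.1 at r = .7 and negligible at r = .85, with one qualifying prior reading; several qualifying readings shift these figures. The sizes rest on an assumed mean and SD, so the direction on that reading is firmer than the amount. Under decay with a stable A1c, Phase 1 holds little more than half of the regression.

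A reader might extend the worry to the primary analysis. The documents do not support that: both arms pass the same cuts before randomisation, so regression to the mean cancels in the Phase 1 between-arm contrast.

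**What to change.** In sections 4 and 5:

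1. Label both cross-period contrasts descriptive, state whether levels or 6-month changes are used, and name regression to the mean and calendar time as limitations.
2. Carry the comparison that section 2 already intends into section 5: a randomised, concurrent between-arm comparison of A1c at 9 and 12 months, adjusted for baseline A1c, as the inferential Phase 2 result. Describe it as a comparison of sequences (early package with calls and letters followed by text reminders, against delayed materials only) that isolates neither calls nor materials.
3. Optionally, show the first contrast net of the control arm's Phase 1 change as a sensitivity figure, stating that it is free of this bias only if the correlation is constant over time.

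The cost is wording and a modest amount of analysis; the measures table in section 4 already schedules A1c at 9 and 12 months. The downside is that the materials-only effect becomes descriptive.
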